7.11.3. Secondary Efficacy Endpoints

Duration of mechanical ventilation and length of hospital ICU stay during the first 21 days post-randomization will be summarized descriptively and compared between treatment groups using a Wilcoxon rank sum test in the MITT, ITT, and PP Populations.

The other secondary endpoint, 28-day all-cause mortality in the ITT, MITT and PP Population, will be descriptively summarized by treatment group. All-cause mortality rate at Day 28 based on Kaplan-Meier estimates along with the 95% confidence interval will also be presented for each treatment group. Subjects whose survival status are unknown

due to early termination or who are lost to follow up will be censored at the last day the subject was known to be alive.

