### 10.2.3 Analysis of Efficacy

The primary efficacy endpoint is whether the subject has developed *S. aureus* pneumonia up to but not including Day 22. The summary measure for efficacy is the proportion of subjects in the MITT Population who develop *S. aureus* pneumonia up to but not including Day 22. Analysis for the primary endpoint will compare the proportion of subjects who develop *S. aureus* pneumonia in the ASN100 arm versus the placebo arm in the MITT Population. The statistical test for comparing 2 event rates is based on a 2-sided test with a false positive rate of 5%.

Analyses of the primary efficacy endpoint will also be performed separately for the ITT and PP Populations.

Duration of mechanical ventilation and length of hospital ICU stay during the first 21 days post-randomization will be compared between treatment groups using a Wilcoxon rank sum test.

Other efficacy endpoints will be summarized by treatment group.

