To ensure balance among the treatment groups, randomization for this study will be stratified by receipt or non-receipt of concomitant anti-staphylococcal antibiotics at the time of randomization that are potentially active against *S. aureus* pneumonia, including, but not limited to, nafcillin, oxacillin, vancomycin, linezolid, telavancin, ceftaroline, ceftobiprole, and teicoplanin.

Following randomization on Day 1, subjects will receive either a single IV dose of 3600 mg of ASN100 (comprised of separate infusions each of 1800 mg ASN-1 and 1800 mg ASN-2) or matching placebos, per their assigned randomization scheme.

If, as part of routine standard of care, additional respiratory and/or other microbiological specimens are collected for culture during the study, results will be documented within the electronic Case Report Form (eCRF). As described within the study laboratory manual, bacterial isolates recovered from these specimens that are deemed pathogens by the

Investigator (if retained and available at the study site's local microbiology laboratory) will be sent to the central microbiology laboratory for confirmation of pathogen identification (all isolates) and susceptibility testing (*S. aureus* isolates only).

Randomized subjects will be monitored daily for the signs and symptoms of pneumonia and other *S. aureus*-associated infections while hospitalized up to up to but not including Day 22.

All randomized subjects will undergo a study visit on Day 22 (+2 days) for treatment efficacy evaluation. A follow-up visit will occur on Day 28 (+2 days) to assess mortality. This visit may be conducted via telephone if the subject is no longer hospitalized.

For subjects who remain hospitalized between Day 40 and Day 90 at the institution where they received study treatment, a follow-up safety visit will be performed on the day of discharge from the hospital during this period.

All randomized subjects will return for a Safety Visit on Day 90 (± 7 days) (if the subject is unable to return to the site, this visit may be conducted by telephone). Subjects who discontinue the study prior to Day 22 will undergo an Early Termination Visit. The end of the study will occur upon completion of the last Day 90 visit by the last subject.

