4.5. Randomization and Blinding

Randomization will occur at the Randomization Visit following determination of the subject's eligibility. Subjects will be randomized via a centralized Interactive Response Technology (IRT) system in a 1:1 ratio to receive a single dose (2 infusions) of either ASN100 or matching placebo. Randomization will be stratified by receipt or non-receipt of concomitant anti-staphylococcal antibiotics at the time of randomization that are potentially effective for the treatment of *S. aureus* pneumonia.

The study follows a double-blind, placebo-controlled design. All study personnel, including investigators, site personnel, site pharmacist, Sponsor and contract research organization (CRO) staff involved in the conduct of the study (e.g., clinical research associate [CRA]/monitor), and subjects will be blinded to treatment assignment, except as described below. ASN100 and placebo will be identical in appearance to preserve blinding.

Randomization data will be kept strictly confidential until the time of unblinding and will not be accessible by subjects, Investigators, or anyone performing assessments and having access to study data until unblinding occurs. An independent Data Review Committee (as described in Section 7.6) will conduct a single interim analysis of futility assessment and will receive unblinded study data. Sponsor and CRO staff who are involved in the conduct of the study will not have access to unblinded Data Review Committee materials. The details of the interim analysis are described in the Data Review Committee Charter dated 8-June-2018. Individual subject unblinding will only occur in the case of subject emergencies or as required by regulations when reporting serious unexpected suspected adverse reactions (SUSARs), with complete unblinding at the conclusion of the study.

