6. SAMPLE SIZE DETERMINATION

The estimated incidence of progression to *S. aureus* pneumonia in mechanically ventilated subjects with heavy endotracheal colonization of *S. aureus* is approximately 25% within 22 days of randomization.

Assuming a 2-sided significance level of 0.05 and a desired power of 80% to detect a significant difference between *S. aureus* pneumonia incidence rates of 25% in the placebo group and 12.5% in the ASN100 treatment group (50% reduction), 152 evaluable subjects are required in each treatment group. A sample size of 304 subjects (152 subjects per treatment group) will yield 80% power to detect a 50% reduction in the incidence of *S. aureus* pneumonia with ASN100 treatment when assuming a 25% incidence rate of *S. aureus* pneumonia in placebo-treated subjects. Assuming a 14% non-evaluable rate, approximately 354 subjects (177 subjects per treatment group) will be randomized. Assuming the screen failure rate is about 84%, approximately 2250 subjects will be screened.

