7. STATISTICAL ANALYSIS

7.1. General Statistical Considerations

Summary statistics will be presented by treatment group. For continuous variables, the number of observations (n), mean, standard deviation (SD), median, minimum, and maximum will be provided. For categorical variables, the frequency and percentage in each category will be displayed.

For summary statistics, the mean and median will be displayed to one decimal place greater than the original value and the measure of variability (e.g., standard deviation) will be displayed to two decimal places greater than the original value.

All statistical tests will be performed at the 0.05 significance level using 2-sided tests, except where otherwise noted. All confidence intervals will have a confidence level of 95%.

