7.11.4. Exploratory Efficacy Endpoints

Exploratory efficacy endpoints include:

- Proportion of subjects in the ITT, MITT and PP Populations with a diagnosis of HABP >48 hours post-extubation up to, but not including, Day 22 in extubated subjects;
- Proportion of subjects in the ITT, MITT and PP Populations with development of VABP up to, but not including, Day 22;
- Incidence of all bacterial pneumonias up to, but not including, Day 22 in the MITT, ITT, and PP Populations;
- Incidence of other non-*S. aureus* pneumonias up to, but not including, Day 22 in the MITT, ITT, and PP Populations; and
- Incidence of other *S. aureus* infections acquired up to, but not including, Day 22 in the MITT, ITT, and PP Populations.
- Mechanical ventilation free days and ICU free days during the first 21 days, or prior to death, or early termination post randomization will be summarized descriptively and compared between treatment groups using a Wilcoxon rank sum test in the MITT, ITT, and PP Populations.
- Summary of pneumonia free days for subjects with *S. aureus* pneumonias, for subjects with bacterial pneumonias, and for subjects with any pneumonia in the MITT and PP Populations.
- Summary of All-cause mortality rate at Day 28 for subjects with any pneumonia in the MITT and PP Populations.

All exploratory efficacy endpoints will be descriptively summarized by treatment group.

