7.12. Subgroup Analyses

The following subgroups will be used for subgroup analyses for the primary efficacy endpoint in the MITT and PP Populations, i.e. whether the subject has or doesn't have of *S. aureus* pneumonia up to, but not including, Day 22 for both SDO1 and SDO2

populations. The exploratory efficacy endpoints, the incidence of all pneumonias, and the incidence of other non-*S. aureus* pneumonias up to, but not including, Day 22 in the MITT and PP Populations, will also undergo the following subgroup analyses.

- Corrected Randomization stratification (Receipt or Non-Receipt of concomitant anti-staphylococcal antibiotics at the time of randomization that are potentially active against *S. aureus* pneumonia.)
- Type of ICU (e.g., SICU, MICU, Neuro ICU, Trauma ICU)
- Type of mechanical ventilation (Tracheotomy or Non-Tracheotomy) at Randomization
- Length of stay in the intensive care unit (ICU) post-treatment (<5, 5-12, >12-22, and >22 days)
- Duration of mechanical ventilation before randomization (48 vs. >48 hours)
- Baseline MRSA/MSSA from qualifying ETA culture
- Pneumonia MRSA/MSSA
- Reason for mechanical ventilation
- BMI categories: <25, 25-<30, 30-<35, and 35
- Age: <50, 50-<65, and >65
- WBC $\times 10^9/L$ at Baseline: <1, 1 to <2.5, 2.5 to <5, 5 to <10, and >10
- Platelet count $\times 10^9/L$ at Baseline: <50, 50 to <150; 150 to <400, and > 400
- Change in platelet count from Baseline: decrease by 50% or greater, or an increase by 50% or greater
- Male vs. female
- Smoker vs. non-smoker
- History of COPD vs. non-COPD
- History of alcohol use vs. no history of alcohol use
- Hospital readmission within 30 days after discharge
- Qualifying ETA and Screening ETA cultures: *S. aureus* only vs. co-colonized *S. aureus* and any Gram-negative at any time before randomization vs. co-colonized *S. aureus* and any other organism at any time before randomization
- Procalcitonin at Baseline for those who develop pneumonia vs. those who don't develop pneumonia: <median vs. median
- Qualifying ETA culture: *S. aureus* 3+ vs. 4+ vs. Heavy
- Cardiac events yes/no from receipt of study drug to Day 90 or early termination
- Multi organ failure yes/no from receipt of study drug to Day 90 or early termination

- Acute kidney injury defined by an absolute increase in serum creatinine of 0.3 mg/dL or a 50% increase (*viz.*, 0.3 mg/dL increase if baseline = 0.6 mg/dL and 50% increase if baseline is = 0.6 mg/dL) within 48 hours from receipt of study drug

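### The four ventilation and ICU day-count comparisons use an unstratified Wilcoxon test although randomization is stratified; stratifying is nearly free and gains power if antibiotic receipt is prognostic

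*SAP*

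**What the plan says.** **Test.** Protocol 10.2.3 says that ventilation duration and ICU stay over the first 21 days "will be compared between treatment groups using a Wilcoxon rank sum test". SAP 7.11.3 likewise compares them "using a Wilcoxon rank sum test", for the MITT, ITT and PP Populations. SAP 7.11.4 adds ventilator-free and ICU-free days, also "compared between treatment groups using a Wilcoxon rank sum test in the MITT, ITT, and PP Populations". None of the three places names a stratum or covariate. SAP 7.1 sets the level: "All statistical tests will be performed at the 0.05 significance level using 2-sided tests, except where otherwise noted".

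**Randomization.** SAP 4.5 states: "Randomization will be stratified by receipt or non-receipt of concomitant anti-staphylococcal antibiotics at the time of randomization". SAP 4.2 and Protocol 5.2 say the same. The aim given in SAP 4.2 and Protocol 5.2 is balance between the arms.

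**Where the stratum is used.** SAP 7.8 lists a corrected version of the factor as a baseline descriptor. SAP 7.12 lists it as a subgroup, "Corrected Randomization stratification (Receipt or Non-Receipt of concomitant anti-staphylococcal antibiotics at the time of randomization", for the primary endpoint and two exploratory pneumonia endpoints. It enters none of the four day-count comparisons, and SAP Section 9 adds no stratified version of them.

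**The concern.** Stratified allocation balances the arms within each antibiotic stratum, so a difference between strata adds almost nothing to the sampling variation of the treatment comparison. An unstratified rank-sum test still counts that difference in its null variance. If patients on these antibiotics at randomization have systematically longer or shorter ventilation or ICU stays, the standard error is too large for the design, the p-value tends to be too large, and power is lost.

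Ventilation duration and ICU stay are the only secondary efficacy endpoints for which SAP 7.11.3 names a between-arm test. 28-day mortality is summarized by arm with Kaplan-Meier estimates and confidence intervals.

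**Working it through.** **1. The plan's own figure.** SAP Section 6 works from "Assuming a 2-sided significance level of 0.05 and a desired power of 80% to detect a significant difference", with event rates of 25% and 12.5%. Using the pooled-variance formula without continuity correction, and a mean rate of 0.1875:

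n per arm = [1.960 × √(2 × 0.1875 × 0.8125) + 0.8416 × √(0.25 × 0.75 + 0.125 × 0.875)]² / 0.125² = (1.0819 + 0.4586)² / 0.015625 = 151.9, so 152.

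304 / (1 − 0.14) = 353.5, so 354 randomized, or 177 per arm. The figure reproduces, but it concerns the primary endpoint only. The documents give no effect size, SD or power for ventilation or ICU days.

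**2. Approximation by hand.** Take a normal outcome with within-stratum variance 1, stratum prevalence p and a stratum difference of d SD. The comparison varies with variance 1, but the unstratified test assumes 1 + p(1 − p)d². Its true type I error is therefore about 2[1 − Φ(1.96 × √(1 + p(1 − p)d²))]. At p = 0.5:

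- d = 0.5: 1.96 × √1.0625 = 2.020, giving 4.3%
- d = 0.8: 1.96 × √1.16 = 2.111, giving 3.5%
- d = 1.0: 1.96 × √1.25 = 2.191, giving 2.8%

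**3. Simulation.** The inputs from the documents are 1:1 allocation, one two-level stratum, two-sided 0.05, 152 or 177 per arm, and a 21-day window. Everything else is assumed:

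- permuted blocks of 4 within strata and a stratum prevalence of 30% or 50%;
- whole days capped at 21 from a lognormal distribution with median 9 and log-SD 0.8;
- a treatment effect of 0.33 SD on the log scale;
- 4,000 runs per scenario.

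The unstratified test uses z = (W − E)/√V with E = m(N + 1)/2 and tie-corrected V, where W is the rank sum of one arm of size m among N subjects. The van Elteren test uses z = Σw(W − E) / √(Σw²V) over the strata, with w = 1/(stratum size + 1).

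Results at 152 per arm, unstratified / van Elteren:

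| Prevalence | Stratum effect (SD) | Type I error, % | Power, % | Gain, points |
|---|---|---|---|---|
| 30% | 0 | 4.7 / 4.8 | 78.7 / 78.4 | −0.3 |
| 30% | 0.2 | 5.3 / 5.5 | 79.2 / 79.3 | +0.1 |
| 30% | 0.5 | 4.5 / 5.1 | 78.3 / 79.4 | +1.1 |
| 30% | 0.8 | 3.3 / 4.4 | 74.5 / 78.2 | +3.7 |
| 30% | 1.0 | 3.3 / 5.0 | 72.3 / 77.8 | +5.5 |
| 50% | 0 | 4.8 / 4.7 | 78.4 / 78.1 | −0.3 |
| 50% | 0.2 | 4.6 / 4.9 | 78.5 / 79.0 | +0.5 |
| 50% | 0.5 | 4.4 / 4.7 | 76.8 / 78.3 | +1.5 |
| 50% | 0.8 | 3.2 / 4.9 | 73.7 / 77.8 | +4.1 |
| 50% | 1.0 | 2.8 / 4.9 | 70.3 / 77.4 | +7.1 |

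At 177 per arm the change is within about 0.1 point at 0 and 0.2 SD. The gain is 0.8 to 0.9 points at 0.5 SD, 3.0 to 3.5 at 0.8 SD, and 5.0 to 6.2 at 1.0 SD. Monte Carlo error is about 0.3 points for type I error, √(0.05 × 0.95/4000), and 0.7 points for power, √(0.78 × 0.22/4000). No unstratified type I error exceeds 5% by more than this error explains; the largest, 5.5%, is at 177 per arm and 0.2 SD. The unstratified error rates agree with step 2.

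**4. What these stratum effects mean in days.** In this model a shift of d SD multiplies the median by e^(0.8d). From 9 days, before rounding up and capping, the other stratum's median is 9 × e^0.4 = 13.4 days at 0.5 SD, 9 × e^0.64 = 17.1 at 0.8 SD, and 9 × e^0.8 = 20.0 at 1.0 SD.

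**The case against.** The strongest objection is that nothing in the documents shows the stratum to be prognostic for these outcomes. No stratum prevalence is given, and no relation between antibiotic receipt and ventilation or ICU days. The nearest text, Protocol 1.2, reports little effect of antibiotics on colonization or on ventilator-associated pneumonia, and assumes the treatment effect to be the same with or without them. A noticeable loss needs a stratum effect of 0.8 SD or more, which in the model above is roughly a doubling of the median. The endpoints have no power target, two of the four comparisons are exploratory, the stated purpose of stratification is balance, and protocol and SAP agree on the test for the two secondary endpoints.

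Most of this stands and limits the point. A reader might infer that the p-values are in fact too large and that power is in fact lost. The documents do not support that, because both depend on an association that they do not report. Nor do they support reading this as a threat to validity, since the possible error is in the conservative direction.

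The objection does not show that stratifying is only a matter of taste. Protocol 1.2 does not address whether patients already on these drugs stay longer on the ventilator or in the ICU. The trade-off is also one-sided: without a stratum effect the stratified test gives up at most 0.3 points of power, which is within simulation error, while with a strong effect it recovers several points.

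**Conclusion.** The point holds as a conditional, minor one. The four comparisons ignore the factor used to stratify randomization, and no stratified sensitivity analysis is planned for them. Type I error is not inflated. If antibiotic receipt predicts ventilation or ICU days, the unstratified test is conservative and loses about 0 to 1.5 points of power up to 0.5 SD and about 3 to 7 points at 0.8 to 1.0 SD. If it does not, the two tests perform alike.

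These sizes rest on the assumed outcome distribution, stratum prevalence, block size and treatment effect. The direction does not depend on those details. The primary endpoint's sample size and power are not touched by this calculation.

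**What to change.** Before unblinding, which SAP Section 3 allows for modifications:

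- In SAP 7.11.3 and 7.11.4, name the van Elteren (stratified Wilcoxon) test by antibiotic stratum for ventilation duration, ICU stay, ventilator-free days and ICU-free days.
- State which stratum is used. Balance is built in for the as-randomized stratum, whereas SAP 7.8 and 7.12 use the corrected one. Run the other version as a sensitivity check.
- Record the change in SAP Section 9, since Protocol 10.2.3 names the plain test for the first two endpoints and Section 9 already lists the plain test for the free-day comparisons.
- A stratified Hodges-Lehmann shift with a 95% confidence interval is optional. Day counts capped at 21 will be heavily tied, which makes a shift estimate awkward to interpret.

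The cost is a few lines of SAP text and minor programming. No new data are needed, because the corrected stratum is already planned for the SAP 7.8 and 7.12 summaries and the as-randomized value is fixed at randomization.

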4.1.2. Secondary Objectives

The secondary objectives of this study are the following:

- To compare the duration of mechanical ventilation post-treatment in subjects treated with ASN100 versus placebo;
- To compare the length of stay in the intensive care unit (ICU) post-treatment for subjects treated with ASN100 versus placebo;
- To determine the serum pharmacokinetics (PK) (i.e. maximum serum concentration [C_{max}], time to maximum serum concentration [T_{max}], area under the serum concentration-time curve [AUC], and terminal elimination half-life [$t_{1/2}$]) of ASN-1 and ASN-2 in mechanically ventilated subjects heavily colonized with *S. aureus*; and
- To compare 28-day all-cause mortality in subjects treated with ASN100 versus placebo.

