7.11.2. Additional Analyses for *S. aureus* Pneumonia

Analyses of the primary efficacy endpoint will also be performed based on the ITT and PP Populations.

The following additional analyses will be performed in the MITT and PP Populations:

- The primary efficacy analysis, based on comparing two proportions of subjects who develop *S. aureus* pneumonia by SDO2 up to, but not including, Day 22. If subjects discontinued from the study due to any cause prior to Day 22 it will be considered as not developing *S. aureus* pneumonia for this analysis by SDO2.
- The primary analysis is based on comparing two proportions of subjects who develop *S. aureus* pneumonia by SDO1 up to, but not including, Day 22. For each arm, the empirical proportion is defined by a ratio, which is the number of *S. aureus* pneumonia events divided by the total number of subjects in the arm. The inference about the difference of two population rates is based on the empirical counterpart. Specifically, the point estimate, 95% confidence interval and p-value for the rate difference. If subjects discontinued from the study due to any cause prior to Day 22, it will be considered as developing *S. aureus* pneumonia by SDO1 and SDO2.
- The Kaplan-Meier analysis will be performed for the proportion of subjects who develop *S. aureus* pneumonia by Day 21 as determined by SDO1. The proportion of subjects who develop *S. aureus* pneumonia up to but not including Day 22 will

be obtained from Kaplan-Meier estimates for each treatment group. The inference about the difference of two rates will be made via the Kaplan-Meier estimates and their corresponding variance estimates in the MITT population. The treatment difference of two rates, the corresponding 95% confidence intervals and p-value will be presented. In addition, the number and percentage of subjects who developed *S. aureus* pneumonia or were censored will be summarized. The Kaplan-Meier estimate of event rates evaluated at Day 21 and the corresponding 95% confidence intervals will be presented for each treatment group. Subjects who did not develop *S. aureus* pneumonia, discontinued from the study, or died prior to Day 22 will be considered censored. For the censored subjects, the last assessment date on which the subject did not develop *S. aureus* pneumonia based on the Investigator's assessment will be used as the date of censoring.

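### Comparing 28-day mortality between arms is a secondary objective, but only per-arm rates and intervals are pre-specified, with no between-arm contrast

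*SAP*

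**What the plan says.** SAP 4.1.2 gives as a secondary objective "To compare 28-day all-cause mortality in subjects treated with ASN100 versus placebo". Protocol 2.2 and the protocol synopsis state the same aim.

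The analysis is in SAP 7.11.3. In the ITT, MITT and PP Populations, 28-day mortality "will be descriptively summarized by treatment group", and a Kaplan-Meier Day-28 rate "along with the 95% confidence interval will also be presented for each treatment group". Subjects with unknown survival status are censored when last known alive. Nothing further is planned for the mortality endpoint.

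The protocol is no fuller. Section 10.2.3 names a Wilcoxon test for ventilation time and ICU stay and then says "Other efficacy endpoints will be summarized by treatment group".

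The only other planned Day-28 mortality analysis is exploratory (SAP 7.11.4, repeated in section 9): "Summary of All-cause mortality rate at Day 28 for subjects with any pneumonia in the MITT and PP Populations". That is a descriptive summary in a subset defined after randomization.

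**The concern.** The stated aim is a contrast between arms, and the planned output is two separate arm summaries. The SAP does not treat its other endpoints this way. In the same section, ventilation time and ICU stay are "compared between treatment groups using a Wilcoxon rank sum test in the MITT, ITT, and PP Populations". In 7.11.2, for the Kaplan-Meier analysis of pneumonia, "The treatment difference of two rates, the corresponding 95% confidence intervals and p-value will be presented". Mortality is the only clinical secondary endpoint with no between-arm result.

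The mortality contrast also helps in reading other results:

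- The primary analysis (7.11.1) counts subjects who discontinue for any cause before Day 22 as free of pneumonia, and the Kaplan-Meier analysis (7.11.2) censors deaths before Day 22. If deaths differ by arm, the pneumonia comparison can be affected.
- Death can shorten ventilation and ICU stay, and 7.11.3 states no rule for deaths in those two tests.

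A planned mortality difference would let a reader judge how far this matters. Without one, whatever contrast appears in the report will have been chosen after the data are known.

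**Working it through.** **1. Search for a contrast.** These are the places where a mortality contrast could appear.

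| Place | What is planned |
|---|---|
| Protocol 10.2.3 | Summary by arm |
| SAP 7.1 | General rules on test level and interval level only |
| SAP 7.11.3 | Summary by arm; Kaplan-Meier rate and interval by arm |
| SAP 7.11.4 | Summary in subjects with pneumonia |
| SAP 7.13.1 | Count by arm of serious adverse events leading to death |
| SAP 9 | Repeats the 7.11.4 summary |

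None gives a difference, ratio, log-rank test or p-value for mortality.

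**2. The plan's own sample size.** SAP section 6 assumes 25% against 12.5% pneumonia, two-sided 0.05 and 80% power. With pooled variance under the null (mean rate 0.1875) and no continuity correction:

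n = [1.960 × √(2 × 0.1875 × 0.8125) + 0.842 × √(0.25 × 0.75 + 0.125 × 0.875)]² / 0.125² = 151.9, so 152 per arm. Power at 152 is 80.0%.

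Allowing for 14% non-evaluable, 304 / 0.86 = 353.5, so 354 randomized, 177 per arm. The stated figures reproduce. They concern pneumonia; no figure is given for mortality.

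**3. Assumptions for mortality.** Control mortality p of 20-30% is assumed, because the documents give none. There are 177 per arm (the randomized number) and little censoring before Day 28, so that a Kaplan-Meier rate behaves like a simple proportion with variance p(1 − p)/177. Let q = p − d be mortality on ASN100.

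**4. Size of reduction each display needs.**

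- The interval for the difference excludes zero when d > 1.96 × √[p(1 − p)/177 + q(1 − q)/177].
- The two arm intervals separate when d > 1.96 × {√[p(1 − p)/177] + √[q(1 − q)/177]}.

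Solving each for d:

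| Control mortality | Difference interval excludes zero | Arm intervals separate |
|---|---|---|
| 20% | 7.6 points | 10.3 points |
| 25% | 8.4 points | 11.4 points |
| 30% | 9.0 points | 12.4 points |

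Check at 30%. For the difference interval, q = 21.0%, the half-widths are 6.75 and 6.00, and √(6.75² + 6.00²) = 9.03. For separation, q = 17.6%, the half-widths are 6.75 and 5.62, and their sum is 12.37. The gap between the two thresholds is about 2.6 to 3.3 points.

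With 152 per arm, in case an analysis population is smaller, the ranges are 8.2-9.7 and 10.9-13.2 points. For an increase in mortality from the same control rates at 177 per arm, they are 8.9-9.9 and 12.8-14.1 points.

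**5. An example.** Take 30% against 20% with 177 per arm. The arm intervals are 23.2-36.8% and 14.1-25.9%, which overlap. The difference is 10.0 points with half-width √(6.75² + 5.89²) = 8.96, so the 95% interval is 1.0 to 19.0 (p = 0.029).

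**6. Power.** At 177 per arm, power for a 20-30% relative reduction from 20-30% control mortality runs from about 16% (20% to 16%) to about 49% (30% to 21%).

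**The case against.** The strongest reply is that nothing is lost. The arms are randomized and independent. Subtracting the two reported rates gives the difference, and with symmetric intervals the root of the summed squared half-widths gives its interval, as step 5 shows. The SAP also follows the protocol, which plans only summaries for endpoints other than ventilation time and ICU stay. These documents use the verb compare loosely: exploratory objectives on HABP, VABP and other *S. aureus* infections use it too and are then only summarized. The trial is Phase 2, sized for pneumonia alone, with many pneumonia analyses already planned and no stated multiplicity procedure. Deaths are also counted by arm in the safety tables.

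Much of this stands. A reader might infer that the objective goes entirely unanswered, or that readers are left to judge by whether the intervals overlap. The documents support neither: the arm rates allow an informal comparison, and no passage tells anyone to use overlap as a test. Low power and the number of other analyses weigh against a confirmatory mortality test. The gap begins in the protocol, so the SAP does not depart from it.

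The omission itself remains. A contrast that each reader works out is neither pre-specified nor reported. It is also only approximate if the Kaplan-Meier intervals are not symmetric, and the SAP does not state their form. Loose wording in exploratory objectives does not explain why one clinical secondary endpoint lacks what the other two have. Low power is no reason to leave out an estimate and its interval.

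**Conclusion.** The point holds as a mismatch between objective and analysis in both documents. A between-arm mortality comparison is promised, and only per-arm results are pre-specified.

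Its size is moderate. A reduction would have to be about 10.3-12.4 points for the arm intervals to separate, against about 7.6-9.0 points for the difference interval to exclude zero. A result between those thresholds would look inconclusive to a reader who sees only the arm intervals. This rests on assumed control mortality of 20-30%, 177 per arm, little censoring and Wald intervals.

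A reader might double the single-arm half-width (5.9-6.8 points at 20-30%) and put the separation threshold for a reduction at about 12-14 points. That requires equal variances in the two arms, which does not hold when the rates differ by that much.

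The change is worth making, but it bears on neither the primary analysis nor the sample size.

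**What to change.** Add one sentence to SAP 7.11.3: the unstratified difference in Day-28 Kaplan-Meier mortality, ASN100 minus placebo, with its 95% confidence interval, in the ITT, MITT and PP Populations. Use the method 7.11.2 already sets out for pneumonia, based on the Kaplan-Meier estimates and their variances. Label the result as estimation, not confirmatory; any p-value is nominal and optional. List it in SAP section 9 as an addition to the protocol analysis.

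Stratifying is not needed. The primary analysis as described in 7.11.1 is unstratified, and stratification would require a weighting rule and a choice between the stratum as randomized and the corrected stratum.

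The cost is one sentence and one table column, with no change to sample size, data collection or conduct. SAP section 3 allows modification before unblinding. The downside is a wide interval: a half-width of about 9 points in the example above.

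Rewording the objective in both documents to describe mortality by arm would also remove the mismatch, but it gives up the comparison now promised.
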